5.2.3 Other baseline characteristics

Other baseline characteristics are not derived but reported as recorded on the eCRF in listings. It includes information collected on:

- 'Smoking status' eCRF (Number of cigarettes a day, Number of years smoked, Year quit, in addition to smoking status baseline characteristics)

5.2.4 Medical history

Medical history includes previous and/or concomitant diseases or diagnoses recorded in the Medical History eCRF. Reported terms are coded using MedDRA (version 21.0). Previous medical history are those diseases or diagnoses with an end date before or equal to the study treatment start date. In the event of a partial end date that overlaps with first dose (e.g., May 2013 and first dose occurred on 23 May 2013) or if an end date is missing, the medical history is considered as previous if ongoing is ticked 'No'. All other medical history terms are considered concomitant. For subjects randomized but not treated the randomization date is used instead of the study treatment start date.

Data originating from the eCRF 'MS History - Complication or Symptoms Associated with MS' are flagged to be summarized separately. No start and stop dates are collected on this page, however, an ongoing (no/yes) at (re-)screening flag is available. If this flag is missing, the complication/symptoms is considered concomitant.

5.2.5 Previous and concomitant therapies

Therapies are collected in the following CRF pages: 'Previous Medications', 'Concomitant Medications', 'MS Specific Treatment History' (List of pre-specified MS specific treatments if ticked as 'Yes') automatically leading to a corresponding record on 'MS Specific Treatment History Log', 'Study-treatment-concomitant Therapy - Disease-modifying Treatment for MS', 'Corticosteroids for Treatment of Relapse'.

Terms are coded using the WHO drug code dictionary and the anatomic therapeutic chemical (ATC) class code (version dated 1 March 2018 or later).

Handling of partial or missing start and end dates is detailed in Section [12.1](#).

5.2.5.1 Previous therapies

Previous therapies are therapies that were started and stopped prior to study treatment start date.

5.2.5.2 Study concomitant therapies: taken between study treatment start and EOS

Includes all therapies that have been taken after study treatment start date up to EOS. This includes therapies ongoing at study start, as well as therapies starting after study treatment start date, or after study treatment end date.

5.2.5.3 Treatment concomitant therapies: taken between study treatment start and EOT

Includes all therapies that have been taken after study treatment start date up to EOT (last drug intake). This includes therapies ongoing at study start, as well as therapies starting after study treatment start date.

In addition, the following are flagged in the datasets:

- *Therapies starting during study treatment administration:* Derived as treatment concomitant therapies starting on or after study treatment start.
- *Therapies ongoing at study treatment start:* Includes all treatment concomitant therapies that started prior to study treatment start, i.e. have not been started during study treatment administration.
- *Therapies taken between study treatment start and EOT + 15 days:* Includes all study concomitant therapies with start date prior to EOT + 15 days. It reflects the therapies taken during the period defining treatment-emergent used for safety reporting.

Handling of partial or missing start and end dates is detailed in Section [12.1](#).

5.2.5.4 Therapies starting after EOT

Includes all study concomitant therapies that have been started after EOT (last drug intake). This includes therapies with start date from EOT + 1 day onwards.

Handling of partial or missing start and end dates is detailed in Section [12.1](#). Therapies with missing start date will be considered to have started on treatment.

5.2.5.5 Disease modifying therapies for MS (DMTs)

Disease modifying therapies are defined as therapies which can favorably alter the course of the disease by reducing the rate and severity of relapses or delaying disease progression by preventing accumulation of disability. For this statistical analyses, DMTs will be identified on an ingredient level if containing any of the text indicated in [Table 5](#) below. Medications in ATC class S (sensory organs, i.e., ophthalmologicals and/or otologicals) will not be considered.

In addition, any other potential DMT, i.e. medications with preferred drug name “INVESTIGATIONAL DRUG” or “BLINDED THERAPY” for Multiple sclerosis (recorded either on the ‘Study-treatment-concomitant therapy - Disease-modifying’ or ‘MS Specific Treatment History Log’ eCRF) will also be taken into account.

Table 5 Disease modifying therapies for MS

ALEMTUZUMAB	MITOXANTRONE
AZATHIOPRINE	MYCOPHENOLIC ACID
CERALIFIMOD	NATALIZUMAB
CICLOSPORIN	OCRELIZUMAB
CLADRIBINE	OFATUMUMAB
CYCLOPHOSPHAMIDE	OZANIMOD
DACLIZUMAB	PEGINTERFERON BETA-1A
DIMETHYL FUMARATE	PLOVAMER
FINGOLIMOD	PLOVAMER ACETATE
GLATIRAMER ACETATE	RITUXIMAB
INTERFERON BETA-1A	SECUKINUMAB
INTERFERON BETA-1B	TERIFLUNOMIDE
LAQUINIMOD	SIPONIMOD
METHOTREXATE	IMMUNOGLOBULINS NOS
INTERFERON ALFA	ETRASIMOD

A text search in ingredients will be conducted: Include all medications containing any of the text above to ensure salts (e.g., “Fingolimod Hydrochloride”) and combination therapies are included.

Start of alternative DMTs for MS (required for efficacy analysis):

For each subject receiving study concomitant DMTs the start date is defined as the first start date of any study concomitant DMT.

Imputation of partial start date is detailed in Section 12.1.1. Missing start dates will not be imputed, consequently therapies with missing start date will not be considered in efficacy analyses up to start of alternative DMTs for MS.

Note on previous DMTs: Occurrence of previous DMTs (stopped prior to ICF consent) is assessed systematically (Yes/No tick boxes) in the ‘MS Specific Treatment History’ eCRF for selected medications. However, for reporting purposes, medications are identified via coding as specified above. On the ‘MS Specific Treatment History Log’ the ‘reason for discontinuation’ (free text) is collected and will be included in listings of MS specific therapies.

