5.4.1.2.5 ARR up to the start of alternative DMTs for MS

This variable considers confirmed relapses up to the point where an alternative disease modifying treatments (DMT) for MS is started as follows:

- The subject's number of confirmed relapses from date of randomization up to the day before the start of new DMT for MS or up to EOS date for subjects not starting a new DMT;
- Length of observation expressed in years, defined as: $[\text{Min}(\text{Day before start date of new DMT for MS, date of EOS}) - \text{date of randomization} + 1]$ in days, divided by 365.25.

Start of alternative DMTs for MS is defined in Section 5.2.5.4 and based on study concomitant MS specific therapies. Variables will be derived separately for confirmed and all relapses.

5.4.1.2.6 *ARR up to EOS for imputed confirmed relapses*

Defined in the same way as number of confirmed relapses for the primary analysis unless the confirmation status is missing (e.g., due to the EDSS not being completed). Relapses with missing confirmation status are imputed as confirmed relapses. The length of observation is defined as for the primary analysis.

5.4.1.2.7 *ARR post EOT + 7 days following premature treatment discontinuation*

Defined for subjects prematurely discontinuing treatment with EOS date after EOT + 7 days:

- The subject's number of confirmed relapses from EOT + 8 days to EOS;
- Length of observation expressed in years, defined as: $[(\text{EOS date} - \text{EOT date} + 8) + 1]$ in days, divided by 365.25.

5.4.1.2.8 *ARR by period*

ARR is derived per period. Variables are defined separately for confirmed relapses and for all relapses. The following periods are considered:

ARR up to Week 60

Derived in the same way as for the ARR up to EOS but including only confirmed/all relapses with onset date from randomization date up to Day 420. Observation time is the time from randomization until earliest of Day 420 or EOS.

ARR after Week 60

Derived in the same way as for the ARR up to EOS but excluding confirmed/all relapses with onset date prior to or on Day 420.

ARR by 12-week periods

Similarly, ARR for approximately 3-month intervals are defined: Baseline to Week 12 (Day 1–84), Week 13 to Week 24 (Day 85–168), Week 25 to Week 36 (Day 169–252), Week 37 to Week 48 (Day 253–336), Week 49 to Week 60 (Day 337–420), Week 61 to

Week 72 (Day 421–504), Week 73 to Week 84 (Day 505–588), Week 85 to Week 96 (Day 589–672), after Week 96 (\geq Day 673).

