- No treatment taken: Any randomized subject who never received study drug [PD_MM.175] is excluded from the Per Protocol Set;
- Compliance < 80 %, as per compliance based on days on study drug, derived from the eCRF, as described in Section 5.3.2.1, is excluded from the Per Protocol Set

Data will be excluded from the per protocol analysis for subjects after the occurrence of one of the following criteria:

- **Subject received wrong study treatment or incorrect dose:**

- Wrong study treatment taken for > 14 days (> 2 consecutive kits as one kit contains 7 doses): Derived as protocol deviation ‘Study drug taken from a non-allocated kit’ [PD_MM.058] and only applies if at least 2 non-allocated kits containing wrong treatment (derived at unblinding: PD_MM.0581) have been taken, exclusion from first intake start date + 14 days onwards. *Note: Wrong study*

treatment taken for ≤ 14 days is not expected to affect efficacy considerably based on pharmacodynamic profile of the study treatment.

- Premature treatment discontinuation: Any randomized subject with premature treatment discontinuation, derived from the eCRF, as described in Section 5.1.5, exclusion from EOT + 7 days onwards.
- **Subject took an unauthorized concomitant medication:**
 - Treatment with systemic corticosteroids and ACTH during treatment, except for MS relapses and short-term treatments with low dose/inhaled corticosteroids for pulmonary conditions defined in study protocol [PD_MM.087], from date of protocol deviation onwards;
 - Any administration of disease modifying therapy for MS during the treatment period [PD_MM.088, PD_MM.093], exclusion from medication start date onwards;
 - During treatment period, any investigational procedure for MS [PD_MM.096], from date of procedure onwards;
- **Occurrence of major protocol deviation that could confound the interpretation of analysis conducted on the FAS;**
 - EDSS assessments not conducted for more than 6 months, exclusion from ‘last EDSS date prior to 6-month gap + 6 months’ onward; derived from eCRF: time between two consecutive EDSS assessments (or last EDSS assessment and EOS date) is > 6 months (182 days).
 - Subject’s randomized treatment allocation was unblinded. Treatment code broken before unblinding of the study (for a reason not related to management of a clinical event [PD_MM.054], or any other unblinding documented in the IRT/eCRF), exclusion from date of unblinding onwards.

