1.4. Exclusion criteria

Condition	Type	Identifier	Source/Instructions	Additional information expected?	Important PD
Lactating or pregnant woman	P	PD_PP.018	eCRF		Yes
Subject wishing to parent a child during the study	P	PD_PP.019	eCRF		Yes
Evidence of a relapse of MS with onset date < 30 days prior to baseline EDSS or between baseline EDSS and randomization	P	PD_PP.020	eCRF		Yes
Diagnosis of MS with progressive course from onset (i.e. diagnosis of primary progressive MS or progressive relapsing MS)	P	PD_PP.047	eCRF		Yes
Treatment within 7 days prior to randomization with IFN b-1a, IFN b-1b or glatiramer acetate	P	PD_PP.021	eCRF		Yes
Treatment within 15 days prior to randomization with b-blockers, diltiazem, verapamil, digoxin or any other anti-arrhythmic or HR lowering systemic therapy, cholestyramine or activated charcoal	P	PD_PP.022	eCRF		Yes
Treatment within 30 days prior to randomization with adrenocorticotrophic hormone (ACTH), systemic corticosteroids, dimethyl fumarate or vaccination with live vaccines	P	PD_PP.023	eCRF		Yes
Treatment within 90 days prior to randomization with medication listed in study protocol exclusion criterion 8	P	PD_PP.024	eCRF		Yes
Treatment within 180 days prior to randomization with medication listed in study protocol exclusion criterion 9	P	PD_PP.025	eCRF		Yes

	TPL-100062 Protocol Deviation Code List
Protocol Number: AC-058B301 Acronym: OPTIMUM	

Treatment within 24 months prior to randomization with lymphocyte-depleting biological agents (e.g. rituximab or ocrelizumab) or cladribine	P	PD_PP.026	eCRF	Yes
Treatment at any time prior to randomization with alemtuzumab, mitoxantrone, leflunomide, teriflunomide, fingolimod, ponesimod or other investigational S1P modulators, stem-cell transplantation	P	PD_PP.027	eCRF	Yes
Any infection or infection risk as per exclusion criteria 12, 13 and 14	P	PD_PP.028	eCRF	Yes
Known Progressive Multifocal Leukoencephalopathy (PML) infection / evidence of new neurological symptoms / MRI signs within 6 months prior to randomization compatible with a PML infection diagnosis	P	PD_PP.110	eCRF	Yes
Any malignancy as per exclusion criteria 15 and 16	P	PD_PP.029	eCRF	Yes
Presence of macular edema	P	PD_PP.030	eCRF	Yes
Any cardiovascular condition as per exclusion criterion 18	P	PD_PP.031	eCRF	Yes
Type 1 or 2 diabetes poorly controlled according to investigator's judgment, or diabetes complicated with organ involvement such as nephropathy or retinopathy	P	PD_PP.032	eCRF	Yes

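### The start date of an alternative DMT is not restricted to DMTs begun after randomization, so a DMT already running at first dose gives a zero or negative observation time in the analysis up to new DMT

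*SAP*

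**What the plan says.** SAP 5.2.5.5 gives the date used in the efficacy analyses: "For each subject receiving study concomitant DMTs the start date is defined as the first start date of any study concomitant DMT". It does not require that date to fall after randomization.

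Section 5.2.5.2 defines the class it draws on: "This includes therapies ongoing at study start, as well as therapies starting after study treatment start date, or after study treatment end date". Under Table 11 (12.1), any record that meets none of the rows for previous therapy is study concomitant by default.

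Section 5.4.1.2.5 counts confirmed relapses "up to the day before the start of new DMT for MS or up to EOS date for subjects not starting a new DMT". The time in years is the minimum of ("Day before start date of new DMT for MS, date of EOS"), minus the randomization date, plus 1 day, divided by 365.25. The variable is "based on study concomitant MS specific therapies". Section 9.6.5.4 uses the log of this time as the offset. Neither section sets a floor.

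Section 7.1.3 has a parallel cut-off for the per-protocol analysis: "Any administration of disease modifying therapy for MS during the treatment period [PD_MM.088, PD_MM.093], exclusion from medication start date onwards". Section 5.4.1.2.4 then puts that date in place of EOS.

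**The concern.** The analysis is meant to stop follow-up when a subject switches to a new therapy. Sections 5.4.1.2.5 and 9.6.5.4 speak of a new DMT, and the estimand note in 9.6.1 places the event after discontinuation of study treatment. The operational definition also picks up old DMTs.

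The SAP foresees such records. Section 5.2.2 has rules for DMTs marked as ongoing at the start of treatment, and the DMT listing in 9.4.5.1 flags them.

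A subject with such a record cannot enter the model, or is cut at the old start date even if a truly new DMT began later. This analysis is one line of the forest plot of main supplementary results (9.6.5.8), and 9.6.5.4 uses it to judge whether the decision to start a DMT biased the FAS result. Subjects who never switched would leave a FAS analysis without any stated rule.

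**Working it through.** **Formula.** Let R be the randomization date and S the DMT start date after imputation. Section 5.4.1.2.5 gives

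T (days) = [min(S - 1, EOS) - R] + 1.

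Whenever S - 1 is not later than EOS, this reduces to T = S - R. T is therefore positive only if S is later than R. The plan states no figure to reproduce.

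**Which old DMTs are study concomitant** (5.2.5.1, 5.2.5.2, Table 11):
- Still taken at first dose: yes.
- On a concomitant form with a missing end date: yes, since no row for previous therapy covers it.
- On a concomitant form with a partial end date spanning first dose, and not marked as not ongoing: yes.
- Clearly stopped before first dose: no, it is previous.

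**Imputation of a partial start date** (12.1.1): the lower limit if the therapy is ongoing at treatment start; otherwise the later of the lower limit and treatment start. First dose is planned for the randomization day (2.1.1).

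**Example** (dates assumed: R = 15 Jun 2016, first dose on R unless stated, EOS = R + 785 days):

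| DMT record | S | T (days) | T (years) | log T |
|---|---|---|---|---|
| Ongoing, begun 200 days before R | R - 200 | -200 | -0.548 | undefined |
| Ongoing, begun the day before R | R - 1 | -1 | -0.003 | undefined |
| Partial start June 2016, ongoing | 1 Jun 2016 | -14 | -0.038 | undefined |
| Partial start June 2016, not ongoing | R | 0 | 0 | undefined |
| Same, first dose one day after R | R + 1 | 1 | 0.003 | -5.901 |
| Truly new DMT | R + 400 | 400 | 1.095 | 0.091 |

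With no new DMT the subject should be followed to EOS: 785 + 1 = 786 days, and 786 / 365.25 = 2.152 years.

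Section 10.1.1 itself notes, for CUAL imputation, that with zero follow-up the log offset does not exist and the record is ignored in the model fit. No handling is given here.

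**Per-protocol cut-off.** With the exclusion date in place of EOS, time is S - R + 1. For S = R - 200 that is -199 days. The pre-randomization exclusions listed in 7.1.3 include PD_PP.024 to PD_PP.027 but not PD_PP.021 (interferon beta, glatiramer acetate) or PD_PP.023 (which covers dimethyl fumarate). The list therefore does not remove such a subject from the PPS.

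**Cross-reference.** Section 5.4.1.2.5 points to 5.2.5.4, which concerns therapies begun after EOT. Taken literally, that would exclude old DMTs. But 5.2.2 cites 5.2.5.4 twice for DMTs taken before randomization, where that meaning is impossible. The definition stands in 5.2.5.5, so this is an outdated section number and not a safeguard.

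**The case against.** The strongest reply is that the intent is plain and the gap is one missing clause. The operative sections say new DMT, a negative time would show up in programming, and the forest plot prints the number of subjects, so a loss would be visible. All true. But the rule as written gives an invalid value, and the repair would then be chosen at the programming stage instead of being fixed in the plan.

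Second, much is already handled:
- A DMT with a completely missing start date is ignored (5.2.5.5).
- Incompletely dated records on the history forms are mostly classed as previous (Table 11, first row).
- A concomitant-form record with a partial end date, marked as not ongoing and with a confirmed earlier start, is also previous.
- A partial start not flagged as ongoing is never set before treatment start.

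This stands and narrows the point. Lower-limit imputation for an ongoing DMT likewise only changes the size of a time that is already invalid.

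A reader might infer that every washout violator is affected. The SAP does not support that. The deviation code PD_PP.021 reads "Treatment within 7 days prior to randomization with IFN b-1a, IFN b-1b or glatiramer acetate"; such a DMT, if clearly stopped before first dose, is previous and never enters the variable.

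Third, 7.1.3 limits the PPS to subjects without major deviations at or before randomization, and a DMT running at randomization arguably fits that general rule. This is fair, but the explicit list omits the two relevant codes, so the result depends on interpretation.

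**Conclusion.** The definition is wrong as written, and the error is confined. It affects a DMT begun before randomization and still taken at first dose, certain concomitant-form records with a missing or unresolved end date, and partial start dates imputed to the randomization day. For each such subject the offset is undefined and all follow-up is lost from the analysis up to new DMT, 2.152 years in the assumed example.

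The primary analysis runs to EOS and does not use this date, so no doubt falls on it. The reach is one supplementary ARR analysis with its forest plot line, plus the per-protocol cut-off. The SAP does not say how many of the 1133 subjects are affected, and any percentage would be a guess. The number is probably small, because few DMTs should still be running, or be left without a usable end date, at first dose. The example dates are assumptions, but the sign of the result is not: T is zero or negative whenever the imputed start is on or before randomization.

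**What to change.** In 5.2.5.5, define the start of alternative DMT as the earliest start date, after imputation, of a study concomitant DMT that is strictly later than the randomization date. State that subjects whose only concomitant DMT began earlier are followed to EOS.

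Add one exception: a DMT whose partial start date is imputed to the randomization date counts, with a minimum observation time of 1 day. This is needed because merely requiring that the DMT is not flagged as ongoing would still leave 0 days in that case. The exception is meant for partial dates whose possible range includes the randomization date.

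In 5.4.1.2.5, correct the reference from 5.2.5.4 to 5.2.5.5.

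In 7.1.3, state that where the medication start date would precede randomization, the subject is excluded from the PPS as having a major deviation at randomization.

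The cost is a few sentences and a small change in the derivation program. No new data are needed, and a DMT truly begun later keeps its present value (400 days in the example).

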5.2.5.6 Corticosteroids for Treatment of Relapse

Corticosteroids for treatment of relapses are medications with preferred drug name from Table 6* recorded on the corresponding eCRF.

Doses of corticosteroids will be converted to prednisone equivalent doses in mg/day and are calculated as described in Table 6 with cumulative dose derived.

Accumulated steroid dose (prednisone equivalent doses in mg) for treatment of relapse from study treatment start (i) up to EOS, and (ii) up to EOT + 7 days are derived for each subject. It is the sum of cumulative steroid dose (mg) across all medications taken in the respective period. Cumulative steroid dose mg per medication is derived as dose mg/day × duration (days). Subjects without steroid use for treatment of relapses have an accumulated dose of 0 mg.

Table 6 Conversion into prednisone-equivalent dose

Corticosteroid	Dose equivalent to 1 mg prednisone	Conversion factor into prednisone equivalent
Prednisone	1 mg	1/1
Cortisone	5 mg	1/5
Hydrocortisone	4 mg	1/4
Prednisolone	1 mg	1/1
Triamcinolone	0.8 mg	1/0.8
Methylprednisolone	0.8 mg	1/0.8
Dexamethasone	0.15 mg	1/0.15
Betamethasone	0.12 mg	1/0.12

*Corresponding salts, i.e., preferred drug name starting with the listed terms are considered as well and corresponding dose is converted in the same way.
Source: GlobalRPh.

5.2.5.7 Beta blocking agents

Beta blocking agents are defined as medications with WHO Drug ATC level 2 code C07: “BETA BLOCKING AGENTS”. It presents a sub-class of ATC class C ‘cardiovascular system’.

5.2.5.8 Therapies used for accelerated elimination

Defined as medications to be used for the protocol mandated accelerated elimination procedure for teriflunomide following treatment discontinuation, i.e., preferred drug names “COLESTYRAMINE” or “CHARCOAL, ACTIVATED”.

